11.1.3 Adverse Events of Special Interest (AESI)

AESIs are a subset of Events to Monitor (EtMs) of scientific and medical concern specific to the product, for which ongoing monitoring and rapid communication by the site investigator to Hoosier Cancer Research Network who will then report to GNE is required. Such an event might require further investigation in order to characterize and understand it. Depending on the nature of the event, rapid communication by the trial Sponsor to other parties (e.g., Regulatory Authorities) may also be warranted.

The following AEs are considered of special interest:

- Cases of potential drug-induced liver injury that include an elevated ALT or AST in combination with either an elevated bilirubin or clinical jaundice, as defined by Hy's Law and based on the following observations:
 - Treatment-emergent ALT or AST $> 3 \times$ ULN (or $> 3 \times$ baseline value in disease states where LFTs may be elevated at baseline) in combination with total bilirubin $> 2 \times$ ULN (of which $\geq 35\%$ is direct bilirubin)
 - Treatment-emergent ALT or AST $> 3 \times$ ULN (or $> 3 \times$ baseline value in disease states where LFTs may be elevated at baseline) in combination with clinical jaundice
- Data related to a suspected transmission of an infectious agent by the study treatment, as defined below
 - Any organism, virus, or infectious particle (e.g., prion protein transmitting transmissible spongiform encephalopathy), pathogenic or non-pathogenic, is considered an infectious agent. A transmission of an infectious agent may be suspected from clinical symptoms or laboratory findings that indicate an infection in a patient exposed to a medicinal product. This term applies only when a contamination of study treatment is suspected.
- Systemic lupus erythematosus
- Events suggestive of hypersensitivity, infusion-related reactions, cytokine release syndrome, macrophage activating syndrome and hemophagocytic lymphohistiocytosis
- Nephritis
- Ocular toxicities (e.g. uveitis, retinitis, optic neuritis)
- Grade ≥ 2 cardiac disorders (e.g. atrial fibrillation, myocarditis, pericarditis)
- Vasculitis
- Autoimmune hemolytic anemia
- Severe cutaneous reactions (e.g., Stevens-Johnson syndrome, dermatitis bullous, toxic epidermal necrolysis)

11.2 Assessment of Adverse Events

All AEs and SAEs whether volunteered by the subject, discovered by study personnel during questioning, or detected through physical examination, laboratory test, or other means will be reported appropriately. Each reported AE or SAE will be described by its duration (i.e., start and end dates), regulatory seriousness criteria if applicable, suspected relationship to the atezolizumab, carboplatin and etoposide (see following guidance), and actions taken. To ensure consistency of AE and SAE causality assessments, investigators should apply the following general guideline:

11.2.1 Relatedness

For patients receiving combination therapy, causality will be assessed individually for each protocol-mandated therapy. AEs will be categorized according to the likelihood that they are related to the study drug(s). Specifically, they will be categorized using the following terms:

Unrelated	Adverse Event is not related to the study drug(s)
Unlikely	Adverse Event is doubtfully related to the study drug(s)
Possible	Adverse Event may be related to the study drug(s)
Probable	Adverse Event is likely related to the study drug(s)
Definite	Adverse Event is clearly related to the study drug(s)

Yes (Definite/Probable/Possible/Unlikely)

There is a plausible temporal relationship between the onset of the AE and administration of atezolizumab, carboplatin or etoposide and the AE cannot be readily explained by the subject's clinical state, intercurrent illness, or concomitant therapies; and/or the AE follows a known pattern of response to atezolizumab, carboplatin or etoposide or with similar treatments; and/or the AE abates or resolves upon discontinuation of the atezolizumab, carboplatin or etoposide or dose reduction and, if applicable, reappears upon re- challenge.

No (Unrelated)

Evidence exists that the AE has an etiology other than the atezolizumab, carboplatin or etoposide (e.g., preexisting medical condition, underlying disease, intercurrent illness, or concomitant medication); and/or the AE has no plausible temporal relationship to atezolizumab, carboplatin or etoposide administration (e.g., cancer diagnosed 2 days after first dose of study drug).

11.2.2 Assessment of Adverse Events (Expectedness)

Expected Adverse Events

For atezolizumab, expected adverse events are those adverse events that are listed or characterized in the current Investigator Brochure (I.B). For carboplatin and etoposide, expected adverse events are those adverse events that are listed or characterized in the Package Insert (P.I).

Unexpected Adverse Event

For this study, an AE is considered unexpected when it varies in nature, intensity or frequency from information provided in the current I3, prescribing information or when it is not included in the informed consent document as a potential risk. Unexpected also refers to AEs that are mentioned in the I3 as occurring with a class of drugs or are anticipated from the pharmacological properties of the drug, but are not specifically mentioned as occurring with the particular drug under investigation.

11.2.3 Procedures for Eliciting, Recording and Reporting Adverse Events

Eliciting Adverse Events

A consistent methodology for eliciting AEs at all subject evaluation time points should be adopted. Examples of non-directive questions include:

- “How have you felt since your last clinical visit?”
- “Have you had any new or changed health problems since you were last here?”

Specific Instructions for Recording Adverse Events

Investigators should use correct medical terminology/concepts when reporting AEs or SAEs. Avoid colloquialisms and abbreviations.

Diagnosis vs. Signs and Symptoms

If known at the time of reporting, a diagnosis should be reported rather than individual signs and symptoms (e.g., record only liver failure or hepatitis rather than jaundice, asterixis, and elevated transaminases). However, if a constellation of signs and/or symptoms cannot be medically characterized as a single diagnosis or syndrome at the time of reporting, it is acceptable to report the information that is currently available. If a diagnosis is subsequently established, it should be reported as follow-up information.

Deaths

All deaths that occur during the protocol-specified AE reporting period, regardless of attribution, will be reported to the appropriate parties. When recording a death, the event or condition that caused or contributed to the fatal outcome should be reported as the single medical concept. If the cause of death is unknown and cannot be ascertained at the time of reporting, report “Unexplained Death”

Preexisting Medical Conditions

A preexisting medical condition is one that is present at the start of the study. Such conditions should be reported as medical and surgical history. A preexisting medical condition should be re-assessed throughout the trial and reported as an AE or SAE only if the frequency, severity, or character of the condition worsens during the study. When reporting such events, it is important to convey the concept that the preexisting condition has changed by including applicable descriptors (e.g., “more frequent headaches”).

Hospitalizations for Medical or Surgical Procedures

Any AE that results in hospitalization or prolonged hospitalization should be documented and reported as an SAE. If a subject is hospitalized to undergo a medical or surgical procedure as a result of an AE, the event responsible for the procedure, not the procedure itself, should be reported as the SAE. For example, if a subject is hospitalized to undergo coronary bypass surgery, record the heart condition that necessitated the bypass as the SAE.

Hospitalizations for the following reasons do not require reporting:

- Hospitalization or prolonged hospitalization for diagnostic or elective surgical procedures for preexisting conditions
- Hospitalization or prolonged hospitalization required to allow efficacy measurement for the study or
- Hospitalization or prolonged hospitalization for scheduled therapy of the target disease of the study

11.2.4 Assessment of Severity of Adverse Events

The adverse event severity grading scale for the NCI CTCAE (v5.0 Update current versions) will be used for assessing adverse event severity. Below Table should be used for assessing severity for adverse events that are not specifically listed in the NCI CTCAE.

Adverse Event Severity Grading Scale for Events Not Specifically Listed in NCI CTCAE

Grade	Severity
1	Mild; asymptomatic or mild symptoms; clinical or diagnostic observations only; or intervention not indicated
2	Moderate; minimal, local, or non-invasive intervention indicated; or limiting age-appropriate instrumental activities of daily living a
3	Severe or medically significant, but not immediately life-threatening; hospitalization or prolongation of hospitalization indicated; disabling; or limiting self-care activities of daily living b,c
4	Life-threatening consequences or urgent intervention indicated d
5	Death related to adverse event d

NCI CTCAE = National Cancer Institute Common Terminology Criteria for Adverse Events.

NOTE: Based on the most recent version of NCI CTCAE (v 5.0), which can be found at: http://ctep.cancer.gov/protocolDevelopment/electronic_applications/ctc.htm

- a. Instrumental activities of daily living refer to preparing meals, shopping for groceries or clothes, using the telephone, managing money, etc.
- b. Examples of self-care activities of daily living include bathing, dressing and undressing, feeding oneself, using the toilet, and taking medications, as performed by patients who are not bedridden.
- c. If an event is assessed as a "significant medical event," it must be reported as a serious adverse event
- d. Grade 4 and 5 events must be reported as serious adverse events

11.2 Reporting

The investigator is responsible for ensuring that all AEs and SAEs that are observed or reported during the study are collected and reported to the FDA, appropriate IRB(s), and Genentech, Inc. in accordance with CFR 312.32 (IND Safety Reports).

11.2.1 Adverse Events

- AEs will be recorded from time of signed informed consent until 30 days after discontinuation of study drug(s) or until a new anti-cancer treatment starts, whichever occurs first.
- AEs will be recorded regardless of whether or not they are considered related to the study drug(s).
- All AEs will be recorded in the subject's medical record and on the appropriate study specific eCRF form within the EDC system.

11.2.2 Serious Adverse Events (SAEs)

11.2.2.1 Site Requirements for Reporting SAEs and AESIs to HCRN

- SAEs will be reported from time of signed informed consent until 30 days after discontinuation of study drug(s) or until a new anti-cancer treatment starts, whichever occurs first.
- SAEs will be reported on the SAE Submission Form **within 1 business day** of discovery of the event.
- SAEs include events related and unrelated to the study drug(s).
- All SAEs will be recorded in the subject's medical record and on the appropriate study specific eCRF form within the EDC system.

The site will submit the completed SAE Submission Form to HCRN **within 1 business day** of discovery of the event. The form will be submitted to HCRN electronically to [contact]. The site investigator is responsible for informing the IRB and/or other local regulatory bodies as per local requirements.

The original copy of the SAE Submission Form and the email correspondence must be kept within the study file at the study site.

Once the SAE has resolved (see resolution guidelines listed above), sites must submit a follow-up SAE Submission Form within a reasonable timeframe to HCRN electronically to [contact].

11.2.2.2 HCRN Requirements for Reporting SAEs and AESIs to Genentech

HCRN will report all SAEs and AESIs to Genentech **within 1 business day** of receipt of the SAE Submission Form from a site. Follow-up information will be provided to Genentech as it is received from site. Genentech Drug Safety: [contact] or Email: [contact]

11.3 Other Reportable Events

11.3.1 Pregnancy reports

If a female subject or a female partner of a male subject becomes pregnant while receiving the study drug or within 5 months after the last dose of study drug, an SAE submission form will be completed. The site should report the event **within 1 business day** of discovery of the event to HCRN and HCRN will report the event to Genentech **within 1 business day** of receipt of the SAE submission form. Follow-up to obtain the outcome of the pregnancy should also occur. Abortion, whether accidental, therapeutic, or spontaneous, should always be classified as serious, and reported as an SAE. Similarly, any congenital anomaly/birth defect in a child born to a female subject exposed to the study drug should be reported as an SAE.

If after the 30 day safety visit, the investigator should become aware of a congenital anomaly in a subsequently conceived offspring of a female subject, including pregnancy occurring in the partner of a male study subject, who participated in the study, this should be reported as an SAE from the site to HCRN who will report to Genentech drug Safety.

11.3.2 Post-Study Adverse Events

SAEs occurring after discontinuation of study drugs will be reported as outlined in section 11.2.2 if attributed to prior atezolizumab, carboplatin or etoposide exposure.

11.3.3 Special Situation Reports

In addition to all SAEs, pregnancy reports and AESIs, the following other Special Situations Reports should be collected even in the absence of an Adverse Event and transmitted to HCRN from the site and HCRN to GNE **within thirty (30) calendar days**.

- Data related to the Product usage during breastfeeding
- Data related to overdose, abuse, misuse or medication error (including potentially exposed or intercepted medication errors)
- In addition, reasonable attempts should be made to obtain and submit the age or age group of the patient, in order to be able to identify potential safety signals specific to a particular population

11.3.4 Product Complaints

All Product Complaints (with or without an AE) shall be forwarded to HCRN from the site and HCRN to GNE **within fifteen (15) calendar days of the awareness date**. A Product Complaint is defined as any written or oral information received from a complainant that alleges deficiencies related to identity, quality, safety, strength, purity, reliability, durability, effectiveness, or performance of a product after it has been released and distributed to the commercial market or clinical trial.

All Product Complaints *without* an AE should be reported via call at:
PC [contact] (M-F: 5 am to 5 pm PST)

11.4 Sponsor-Investigator Responsibilities

HCRN will send a SAE summary to the sponsor-investigator **within 1 business day** of receipt of SAE Submission Form from a site. The sponsor-investigator will promptly review the SAE summary and assess for expectedness and relatedness.

11.5 HCRN Responsibilities to FDA

For protocols exempt from the requirements of an IND, the above stated requirements are not applicable. HCRN will continue to facilitate compliance of applicable requirements for the sponsor-investigator in relation to this study. This includes but is not limited to 21 CFR 50.20 informed consent, 21 CFR Part 56 IRB, and pertinent sections of the Public Health Service Act and FDAAA.

11.6 IND Safety Reports Unrelated to this Trial

Genentech will provide to HCRN IND safety reports from external studies that involve the study drug(s) per their guidelines. HCRN will forward safety reports to the sponsor-investigator who will review these reports and determine if revisions are needed to the protocol or consent. HCRN will forward these reports to participating sites **within 1 business day** of receiving the sponsor-investigator's review. Based on the sponsor-investigator's review, applicable changes will be made to the protocol and informed consent document (if required). All IND safety reports will also be made available to sites via the EDC system.

Upon receipt from HCRN, site investigators (or designees) are responsible for submitting these safety reports to their respective IRBs, as per their IRB policies.

12 STATISTICAL METHODS

12.1 Study Design

This is a multicenter, single arm, open label phase II trial to evaluate the safety and efficacy of atezolizumab in combination with carboplatin and etoposide in patients with untreated extended stage small cell lung cancer (ES-SCLC) brain metastases.

12.2 Endpoints

The primary endpoint of the trial is intracranial progression free survival (iPFS).

The secondary endpoints include overall response rate (ORR), intracranial or extracranial progression free survival (PFS), overall survival (OS), and the grade and type of toxicity of atezolizumab in combination with carboplatin and etoposide.

12.2.1 Definition of Primary Endpoint

The primary endpoint of the study is intracranial progression free survival (iPFS), which is defined as the time from Day 1 of protocol treatment until the criteria for iPFS is met as defined by RANO-BM or death from any cause, whichever comes first.

12.2.2 Definition of Secondary Endpoints

ORR is the proportion of patients whose best response to protocol treatment are either complete response (CR) or partial response (PR) by the investigator using RECIST 1.1. Patients not meeting these criteria, including patients without any post-baseline tumor assessment, will be considered non-responders.

PFS is defined as the time from Day 1 of protocol treatment until the criteria for disease progression (intracranial or extracranial) is met as defined by RECIST 1.1 and RANO-BM, or death from any cause, whichever comes first. Subjects who have not progressed will be right-censored at the date of the last disease evaluation. If progression occurs in either intracranial or extracranial or both compartments, the criteria for progression-free survival will have been met per RANO-BM.

OS is defined as the time from Day 1 of protocol treatment until death from any cause.

CTCAE V5 will be utilized to define the grade and type of toxicities and adverse events.

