OBJECTIVES	
Primary Objective
 
1.) Intracranial progression free survival (iPFS)
 
Secondary Objectives
 
1.) Overall response rate (ORR) 2.) Extracranial Progression free survival (PFS) 3.) Overall survival (OS) 4.) Toxicity of atezolizumab plus carboplatin and etoposide
 
Exploratory Objectives
 
1.) Explore circulating biomarkers in patients with SCLC brain metastases 2.) Explore patient-reported quality of life (QoL) 3.) Investigate the immune and genomic landscape of SCLC primaries that metastasized to the brain

STUDY DESIGN	Single arm, multicenter phase II trial for n=60 patients with untreated extensive stage (ES) small cell lung cancer (SCLC) and asymptomatic brain metastases.
KEY ELIGIBILITY CRITERIA (See Section 3 for full eligibility criteria)	
 • Histological confirmation of Small Cell Lung Cancer- Stage IV/Extensive Stage (SCLC) per Veterans Administration Lung Study Group (VALG). • Untreated, asymptomatic brain metastases • No prior systemic therapy for metastatic disease [a single cycle of chemotherapy (platinum/etoposide) with or without atezolizumab is allowed within 30 days prior to enrollment]
STATISTICAL CONSIDERATIONS	A Kaplan-Meier curve will graphically describe iPFS, PFS, and OS among patients treated by at least one cycle of Atezolizumab. Median survival, as well as 6-month iPFS and PFS, and 12-month OS will be estimated with their 95% confidence intervals (CI). The impact of patients' demographics and baseline clinical characteristics on survivals will be evaluated in the context of a Cox PH model. The ORR, the proportion of treated subjects with a complete or partial response, will be calculated with its 95% CI. The

	
association of ORR with patients' demographics and baseline clinical characteristics will be evaluated in a logistic regression model.
 
The quality of life of treated patients at baseline and during treatment will be summarized and the patients' demographics and baseline clinical characteristics on the change of the quality of life will be evaluated in a linear regression.

TOTAL NUMBER OF SUBJECTS	N = 63 eligible patients (60 evaluable)
ESTIMATED ENROLLMENT PERIOD	Estimated 22 months from lead site opening to accrual
ESTIMATED STUDY DURATION	Estimated 40 months

TABLE OF CONTENTS

Schema	6
1. Background and Rationale	7
2. Study Objectives and Endpoints	10
3. Eligibility Criteria	11
4. Subject Registration	15
5. Treatment Plan	15

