2.1.2 Secondary Objectives

- Estimate the overall response rate (ORR) for atezolizumab when administered with carboplatin and etoposide in subjects with untreated SCLC brain metastases
- Estimate the extracranial progression free survival (PFS) for atezolizumab when administered with carboplatin and etoposide in subjects with untreated SCLC brain metastases
- Estimate the overall survival (OS) for atezolizumab when administered with carboplatin and etoposide in subjects with untreated SCLC brain metastases
- Evaluate the toxicity of atezolizumab when administered with carboplatin and etoposide in subjects with untreated SCLC brain metastases

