2.2.2 Secondary Endpoints

- ORR will include complete response (CR) + partial response (PR) as determined by RECIST 1.1.
- Extracranial PFS is defined as the time from Day 1 of treatment until the criteria for extracranial disease progression is met as defined by RECIST 1.1 or death as a result of any cause, whichever comes first.
- OS is defined as the time from Day 1 of treatment until death as a result of any cause.
- Toxicity will be graded by Common Toxicity Criteria for Adverse Events (CTCAE V5).

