12.6.2 Analysis Plans for Secondary Objectives

ORR and its 95% CI will be estimated.

Median PFS and OS and their 95% CIs will be estimated using Kaplan-Meier approach. KM curves will be used to characterize PFS and OS. Six-month PFS and 12-month OS rates and their 95% CIs will also be estimated. Cox proportional hazard models will evaluate the relationship between PFS or OS with the patients' baseline characteristics, including age at enrollment, gender, race, and ECOG Performance Status and the estimated HRs and their 95% CIs will be provided.

The types and frequencies of toxicities will be summarized by the severities.

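### One label, PFS, carries two conflicting definitions: extracranial progression or death in the synopsis and section 2, progression in either compartment or death in section 12

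*Combined protocol and SAP*

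**What the plan says.** The synopsis lists "Extracranial Progression free survival (PFS)" among the secondary objectives. Section 2.1.2 repeats it: "Estimate the extracranial progression free survival (PFS) for atezolizumab when administered with carboplatin and etoposide". Section 2.2.2 defines the endpoint from Day 1 of treatment "until the criteria for extracranial disease progression is met as defined by RECIST 1.1 or death" from any cause. In these places PFS abbreviates the extracranial endpoint.

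Section 12 departs from this. Section 12.2 lists "intracranial or extracranial progression free survival (PFS)" as the secondary endpoint. Section 12.2.2 defines it: "PFS is defined as the time from Day 1 of protocol treatment until the criteria for disease progression (intracranial or extracranial) is met", by RECIST 1.1 and RANO-BM, or death. The same paragraph then says again that progression in either compartment, or in both, satisfies the criterion. Section 12.6.2, the analysis plan for the secondary objectives, states: "Median PFS and OS and their 95% CIs will be estimated using Kaplan-Meier approach". It adds a 6-month PFS rate and Cox models for PFS, and does not name extracranial PFS.

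**The concern.** The two definitions count different events. A patient whose first progression is in the brain alone has an event on that date under 12.2.2 but not under 2.2.2. Such patients are to be expected in a trial of untreated brain metastases.

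Three things are at stake. First, a stated secondary objective would not be estimated as section 2 defines it. Second, section 13.4 requires results for all secondary objectives to be posted, and the PFS result available from section 12 would be a different quantity under the same abbreviation. Third, the trial is open-label with one arm, so an unresolved definition leaves room to choose one after results are known. The label also reaches section 8.2.2, which correlates protein analytes with PFS and OS.

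**Working it through.** The point is settled by comparing the text. The plan states no figure for either version of PFS, so there is none to reproduce.

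**Step 1. Set the texts side by side.**

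| Place | Name used | Event |
|---|---|---|
| Synopsis, objectives | Extracranial PFS | not defined |
| 2.1.2 | Extracranial PFS | not defined |
| 2.2.2 | Extracranial PFS | Extracranial progression (RECIST 1.1) or death |
| 12.2 | Intracranial or extracranial PFS | not defined |
| 12.2.2 | PFS | Progression in either compartment (RECIST 1.1 and RANO-BM) or death |
| 12.6.2 | PFS | as 12.2.2, the only definition in section 12 |

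**Step 2. Test the harmless reading.** The wording in 12.2 could mean two separate endpoints. Section 12.2.2 rules this out, because it defines one endpoint that either compartment can trigger. Intracranial PFS is also already the primary endpoint (12.2.1).

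**Step 3. Direction.** Every event under 2.2.2 is also an event under 12.2.2, but not the reverse. For any fully observed patient, any-site PFS is therefore no longer than extracranial PFS. Reporting one for the other can only understate extracranial PFS.

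**Step 4. Size, as an illustration.** The assumptions, none of them from the documents, are:
- any-site PFS is exponential with median 5.2 months (the documents cite 5.2 months as the PFS of the atezolizumab arm of the phase III trial);
- a share s of first any-site events is intracranial progression alone;
- the two hazards are independent, and extracranial PFS is censored at intracranial progression.

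The any-site hazard is h = ln 2 / 5.2 = 0.1333 per month. The extracranial hazard is h(1 − s), so the median is 5.2/(1 − s) and the 6-month rate is exp(−6h(1 − s)).

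| s | Median (months) | 6-month rate |
|---|---|---|
| 0 (any-site PFS) | 5.2 | 44.9% |
| 0.10 | 5.2/0.9 = 5.8 | 48.7% |
| 0.20 | 5.2/0.8 = 6.5 | 52.7% |
| 0.30 | 5.2/0.7 = 7.4 | 57.1% |
| 0.40 | 5.2/0.6 = 8.7 | 61.9% |

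The gap runs from about 0.6 to 3.5 months in the median and from 4 to 17 points in the 6-month rate.

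**Step 5. Can extracranial PFS be observed after brain progression?** Footnote 5 to the study calendar has follow-up tumour evaluations documented until progression, death or another treatment. Footnote 11 requires continued imaging only for patients who stop for reasons other than progression, and moves patients to survival follow-up once progression is documented. Neither names the site. Section 1.4 lets patients take standard care and radiation off study at progression. Extracranial progression after brain-only progression may therefore go unseen, and no section says how such a patient enters the extracranial endpoint.

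**The case against.** The strongest defence is that extracranial PFS does have an analysis. The synopsis and 2.1.2 introduce PFS as its abbreviation, and the synopsis and 12.6.2 then plan Kaplan-Meier estimates of PFS. This stands in part. A reader might infer that the objective has no analysis at all, which is too strong: the defect is one label with two definitions. The defence does not remove the problem, because the statistical section defines PFS itself and defines it as any-site.

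It is also fair that 12.2.2 states its definition openly, that the endpoint is descriptive with no test or stopping rule attached, and that 12.3 disclaims power for secondary endpoints. Reporting under the wrong name is thus an inference from the shared label and the posting duty, not something the plan says.

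Two further inferences are tempting and unsupported. One is that the repair is only wording because the data are already collected. Footnotes 5 and 11 do not secure extracranial imaging after brain progression. The other is a dramatic size. If each compartment's endpoint had a 5.2-month median and no hazard were shared, any-site PFS would have a median of 5.2/2 = 2.6 months. Both endpoints count death from any cause, so some hazard must be shared and 2.6 is only a mathematical limit. Nor do the documents give any extracranial median. Setting such a gap against the 1.2-month design effect (5.2 − 4.0) would also mislead, because that effect belongs to intracranial PFS.

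**Conclusion.** The point holds as a conflict of definitions. Sections 2 and 12 disagree on the event, and no other text reconciles them. If section 12 is followed, any-site PFS stands in for the extracranial endpoint that the protocol promises.

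The direction of the difference follows from the definitions. Its size is unknown: the ranges in step 4 rest on an assumed any-site median, an assumed 10% to 40% brain-only share, exponential and independent hazards, and censoring at intracranial progression. The documents do not show which definition was intended. The primary endpoint, its sample size and the futility rule are untouched. This should be corrected, but it does not threaten the trial's main conclusion.

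**What to change.** Use distinct names throughout. In 12.2, 12.2.2 and 12.6.2, define and analyse extracranial PFS as 2.2.2 has it, and keep the present 12.2.2 definition as a separately named any-site PFS. Carry both names into the synopsis, section 2 and section 8.2.2. Aligning both sections on one definition would also end the contradiction, but choosing any-site alone would drop a stated objective.

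Renaming is not enough. State in advance how extracranial PFS treats a patient who progresses first in the brain. One option is to treat intracranial progression as a competing event and report cumulative incidence. Another is to censor at the last extracranial assessment and add a sensitivity analysis. If scans stop at progression, that censoring falls in practice at brain progression and is likely to be informative. State also whether a later death counts: 2.2.2 counts death from any cause, and survival follow-up continues after progression.

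The cost is a protocol and SAP wording change, one more Kaplan-Meier or cumulative-incidence table, and a stated limitation that extracranial progression after brain progression may not be observed, because the calendar footnotes require no scans once progression is documented.
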